# 4.0 Study Endpoints\*

The specific aim is to investigate the reliability of accurately measuring the concentration of ciprofloxacin from aspirates of middle ear fluid after self-administration of otic drops in subjects with chronic otorrhea. A secondary aim is to correlate these concentrations with patient factors such as the extent of otorrhea and the anatomy of the ear.

Objective	Study Endpoint	Safety Endpoint
Investigate the reliability of measuring concentration of ciprofloxacin from middle ear aspirates	Precise sampling of a known aspirate volume (100 microliters) and performance of LC-MS/MS ciprofloxacin assay development for middle ear aspirate analysis	
Correlate the concentrations with patient factors	Correlate ciprofloxacin concentration of middle ear aspirate to symptom resolution time, patient demographics, patient anatomy and clinical outcomes (infection resolution).	

# 5.0 Study Intervention/Investigational Agent

The standard of care for CSOM involves ototopical quinolone therapy such as ciprofloxacin or ofloxacin. The affected ear is routinely cleaned of any debris, and a Juhn Tym-Tap® device will be used to aspirate fluid for culture samples. The patient will be provided the standard course of treatment, which is a prescription

for antibiotic drops of ciprofloxacin 0.3% and dexamethasone 0.1% suspension with specific written instructions. The frequency of treatment is three times daily for ten days.

For this study, patients who meet inclusion-exclusion criteria will be offered an opportunity to participate by the prescribing provider. Informed consent will be obtained. Enrolled subjects will be asked to return 3 to 10 days after the initial visit. Additionally, the subject will be asked to keep a log of their medication use and to administer the ototopical medication one hour prior to their appointment. During the follow-up appointment, the ear will be cleaned of any wax or purulent debris. A microscopic aspirate (~100 µL) will then be collected of fluid at the level of the non-intact tympanic membrane will be collected using with a modified Juhn Tym-Tap®. This type of sampling of middle ear aspirates is commonly performed in the ENT clinic (performed more than 120 times in the Dartmouth-Hitchcock ENT clinic in the past year). After sampling, the volume of the aspirate will then be precisely measured with a device developed specifically for this study. The color and consistency of the sample will be noted. The sample will then be diluted with a known volume of water to an acceptable volume for the LC-MS/MS assay. Furthermore, other data beyond ciprofloxacin concentration such as otologic diagnosis, bacteria culture results, presenting symptoms, specific site of infection, external ear canal volume estimates (based upon tympanometry and physical exam), configuration of external auditory canal, prescribed treatment, treatment outcome, and duration of infection will be noted for each subject.

## 6.0 Procedures Involved\*

Specimen collection: This will be a prospective observational study of adult subjects being diagnosed with chronic otorrhea at a tertiary care hospital, Dartmouth-Hitchcock Medical Center. To test our hypothesis, we will identify subjects with chronic otorrhea in clinic. Informed consent will be obtained. Subjects will be given a prescription for antibiotic drops containing ciprofloxacin 0.3% and dexamethasone 0.1% suspension from a pharmacy of their choice with specific written instructions for self-administration. A compliance card will be given to record adherence to three-time daily regiment for ten days. Drops will be dosed three times daily for ten days, and no other non-prescribed ototopical antibiotic therapy nor additional over the counter treatments should be used during this period. Subjects will return for a follow up visit between 3 to 10 days after their initial visit and will be asked to administer the drops in the affected ear one hour prior to their appointment. At that time, the ear will once again be cleaned of any debris and a microscopic aspirate (~100  $\mu$ L) of fluid at the level of the tympanic membrane or middle ear will be collected using an aseptic technique with a Juhn Tym-Tap specimen trap to collect micro aspirates. This specimen will be analyzed, precisely measured for

volume, diluted, and sent for analysis using mass spectrometry (description below). Data collected will include patient demographics, otologic diagnosis, bacteria culture results, presenting symptoms, amount and type of drainage, specific site of infection, external ear canal volume estimates, configuration of the external auditory canal based on physical exam, prescribed treatment, treatment outcome, and duration of infection.

Ciprofloxacin concentration measurements: A reverse-phase liquid chromatography with tandem mass spectrometry (LC-MS/MS) assay will be developed to measure concentrations of ciprofloxacin in the auricular aspirate. The assay is based on that published by Matta et al (16). In brief, a C18 stationary phase column will be used with a gradient elution of 5mM ammonium formate in 0.1% formic acid buffer and acetonitrile for the mobile phase. External standards using a ciprofloxacin stock solution at low, medium, and high concentrations will be used to create a calibration curve of instrument response to known concentrations. For sample analysis, a 30-µL aliquot of the auricular aspirate sample will be combined with a 60-µL water and 100-µL acetonitrile, which would be spiked with a single standardized amount of the internal standard, deuterated 8 ciprofloxacin. By using this internal standard method of calibration, a precise quantification of the ciprofloxacin concentration in the auricular aspirate will be developed and validated by the staff of the Clinical Pharmacology Shared Resource directed by [name].

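### The aspirate may be taken on any of days 3 to 10, but the concentration-outcome analysis ignores sampling day and ears that resolved before the visit

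*Combined protocol and SAP*

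**What the plan says.** Two sections give the same sampling window. Section 5.0: "Enrolled subjects will be asked to return 3 to 10 days after the initial visit". Section 6.0: "Subjects will return for a follow up visit between 3 to 10 days after their initial visit". The window lies inside the treatment course, for which Section 5.0 states: "The frequency of treatment is three times daily for ten days".

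The time from last dose to sample is meant to be the same for everyone. Subjects "will be asked to administer the drops in the affected ear one hour prior to their appointment". At the visit, "the ear will once again be cleaned of any debris and a microscopic aspirate" of about 100 µL is collected. The assay uses "a 30-µL aliquot of the auricular aspirate sample".

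The secondary endpoint in Section 4.0 is: "Correlate ciprofloxacin concentration of middle ear aspirate to symptom resolution time, patient demographics, patient anatomy and clinical outcomes (infection resolution". The only analysis statement is in Section 17.0: Fisher's exact test, n=10, comparing concentration with demographics, extent of perforation, drainage and treatment outcome.

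The documents do not give a time origin for resolution time, a role for sampling day, or a rule for an ear that is dry or resolved at the visit. Sampling day is not in the data lists of Sections 6.0 and 7.0, although visit dates and the compliance card would supply it.

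**The concern.** Concentration is the explanatory variable, yet it is measured 3 to 10 days after treatment begins, when the outcome may already have occurred. For an ear that resolved before the visit there are two possibilities, and the plan covers neither.

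- **No fluid.** The subject has no concentration and leaves the analysis. Those lost are all early responders. Among those who remain, a subject sampled on day 10 must have a resolution time above 10 days, whereas one sampled on day 3 need only exceed 3. Resolution time is then linked to sampling day by the schedule.
- **Leftover drop fluid.** The subject stays in. Section 3.0 names volume of otorrhea as a factor in drug availability, so a resolved ear with little discharge could give a less diluted sample. A high value would then be paired with a short resolution time because the ear had healed, not because the drug reached it.

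At stake is how any association between concentration and outcome is read, which is the purpose of the secondary aim.

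**Working it through.** The plan gives no figure to reproduce: N=10 is stated without alpha, power, effect size or loss allowance. The figures below illustrate size on stated assumptions.

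**1. Spread of exposure at sampling (from the documents).** Day 3: 3 × 3 = 9 scheduled doses. Day 10: 3 × 10 = 30. Ratio 30/9 = 3.3.

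**2. Share of ears resolved by the visit (assumed inputs).** Resolution time T is log-normal with median m and log-SD 0.7. Visit day V is equally likely to be each of the 8 days from 3 to 10. Then

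P(T ≤ V) = (1/8) × Σ Φ(ln(v/m)/0.7), v = 3, …, 10.

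For m = 10 the eight terms are 0.043, 0.095, 0.161, 0.233, 0.305, 0.375, 0.440 and 0.500. They sum to 2.152, and 2.152/8 = 0.269.

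**3. Effect of losing those ears, with no drift by day.** Time is counted from the initial visit, the true rank correlation of concentration with resolution time is -0.53, and only unresolved ears give a sample. Results are from simulation of 400,000 subjects per setting.

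| Assumed median | Resolved at visit | Expected of 10 | Chance of at least one | Correlation in those sampled |
|---|---|---|---|---|
| 10 days | 27% | 2.7 | 1 − 0.73^10 = 96% | -0.45 |
| 14 days | 15% | 1.5 | 1 − 0.85^10 = 80% | -0.47 |
| 21 days | 6% | 0.6 | 1 − 0.94^10 = 46% | -0.50 |

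A median of 7 days would raise the resolved share to 43%.

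**4. Adding drift by day.** Assume concentration rises by 0.2 SD per treatment day, which is 7 × 0.2 = 1.4 SD across the window. Median 10 days, only unresolved ears sampled:

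| True association | Drift per day | Unadjusted Spearman | Partial Spearman, adjusted for day |
|---|---|---|---|
| -0.53 | none | -0.45 | -0.43 |
| -0.53 | 0.2 SD | -0.29 | -0.42 |
| none | none | 0.00 | 0.00 |
| none | 0.2 SD | +0.12 | 0.00 |

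If every ear gives a sample, drift alone also produces a spurious correlation of 0.00. A false association in this model therefore needs both selection and drift. A downward drift would reverse the sign of the artefact.

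**5. What adjustment does.** It removes the artefact due to sampling day (+0.12 to 0.00, and -0.29 to -0.42). It does not return the estimate to -0.53, because the missing early responders stay missing.

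The leftover-fluid case was not simulated. The documents give nothing from which to set its size.

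**The case against.** Several stronger readings are tempting, and the documents do not support them.

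- *Only wet ears are sampled, so the fastest responders are dropped.* No section says so. Drops go in one hour before the visit, and a resolved ear may still yield fluid. Nor is a short sample necessarily lost: the assay aliquot is 30 µL and dilution is planned. Loss of early responders is a possibility, not a rule of the protocol.
- *The window ties concentration to treatment day.* The dose-to-sample interval is held at about one hour, and the documents give no data on change by day. Drift is assumed here. So is the even spread of visits, since the weekly follow-up in Sections 1.0 and 9.0 might cluster them.
- *Scheduling alone creates an association.* Without drift the spurious correlation is 0.00.
- *The primary feasibility result is overstated.* Section 4.0 defines the primary endpoint as sampling of a known volume and assay development. It sets no success rate or denominator, so there is no figure to overstate.

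Two further objections carry weight. The selection effect alone (0.03 to 0.08 in step 3) is small beside the sampling error of a rank correlation at this size, whose standard deviation is 0.29 to 0.36. With no true association, even a drift of 0.4 SD per day raises the chance of p<0.05 only to 5.6–7.0%, from 5.4–5.7% without drift. The working also uses a rank correlation where the plan names Fisher's exact test. That test needs concentration in categories, and no cut-points are given, so the effect on the planned test itself cannot be computed.

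What stands is the gap: either fate of a resolved ear biases the comparison, and the plan identifies neither.

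**Conclusion.** The concern holds in a limited form. The window, the dose range and the absence of sampling day and resolved ears from the analysis are plain in the text. The size of the bias is not. It depends on the share of ears resolved at the visit (about 6% to 27% for assumed medians of 21 to 10 days), on whether such ears yield fluid, and on any drift by day. With no drift the distortion is slight. With an assumed 0.2 SD per day and a 10-day median, close to half of a true -0.53 disappears ((0.53 − 0.29)/0.53 = 45%).

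The harm is to interpretation of the secondary aim, not a confident false positive. For the primary aim the consequence is limited to reporting how many subjects gave a usable aspirate. The change is worth making because it uses dates the study will already hold.

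**What to change.** Keep the 3 to 10 day window and amend the analysis in Section 17.0.

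1. For concentration against resolution time, replace the unadjusted Fisher's exact test with a partial Spearman correlation adjusted for days on treatment at sampling. State how subjects unresolved when follow-up ends are ranked.
2. Relate concentration only to resolution that occurs after the sampling visit. Show subjects already resolved at that visit separately, with their concentrations where available.
3. Report aspirates obtained out of all enrolled subjects, with the reason for each missing sample. Add a bounding analysis against resolved yes/no that ranks the missing concentrations highest and then lowest.

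Keep drainage at sampling as a candidate factor. Sections 2.0 and 3.0 treat otorrhea as influencing delivery, and a grade from the initial visit would not describe the ear at the time of the dose that was sampled.

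**Cost.** The planned test is replaced for this question, and one degree of freedom is lost at n=10. No visit or sample is added. The adjustment removes the sampling-day artefact but not the selection, which is why items 2 and 3 are needed as well.

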# 1.0 Study Summary

Study Title	Antibiotic concentration after delivery to middle ear for				
	chronic suppurative otitis media				
Study Design	Prospective observational study				
Primary Objective	Investigate the reliability of ciprofloxacin concentration				
	measurements from aspirates of middle ear fluid after self-				
	administration of otic drops in patients with chronic otorrhea				
	and non-intact tympanic membrane				
Secondary	Elucidate the role of antibiotic concentration in varying				
Objective(s)	clinical outcomes in patients with chronic middle ear				
	infections by using antibiotic concentration analysis of				
	aspirates.				
Research	Patients diagnosed with chronic suppurative otitis media				
Intervention(s)/	prescribed with antibiotic drops $(0.3\%$ ciprofloxacin, 0.1%				
Investigational	dexamethasone suspension) will apply drops 1-hour prior to				
Agent(s)	visit. During visit, the ear will be cleaned of any debris and a				
	microscopic aspirate of approximately 100 microliters will				
	be collected with a modified Juhn Tym-Tap device.				
IND/IDE #	N/A				
Study Population	Adults in the community with diagnosed chronic middle ear				
	infection				
Sample Size	N=10				
Study Duration for	An individual participant will be followed on a weekly basis				
individual	until reaching either criteria of complete symptom				
participants	resolution, new treatment prescription, or maximum duration				
	of 3 months				
Study Specific	Chronic suppurative otitis media (CSOM)				
Abbreviations/					
Definitions					

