# 17.0 Data Management\* and Confidentiality

Given the small sample size (n=10) and expected variability of results, a Fisher's exact test will be used to describe and compare the measured concentration of ciprofloxacin at the tympanic membrane to subject demographics as well as extent of perforation, amount of aural drainage and treatment outcomes.

The data will be managed on a locally encrypted device in an Excel file while stored on the encrypted cloud storage service called ShareFile. Access will be provided to those on the research team on a need-to-know basis with particular caution to ensure separation of identifiers and data. Any communication in a non-encrypted platform will not contain any protected health information.

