# 21.0 Economic Burden to Subjects

The subject will have direct time cost by participating in this research including the travel and clinic time associated with the additional ear sampling needed to obtain the studyrelated middle aspirate. This may have an indirect financial cost with time possibly taken off from work. Furthermore, the subjects will be expected to complete a medication compliance / symptoms log. To offset this economic burden, subjects will be compensated \$50 for their participation.

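### The pre-visit drop is timed by the subject to the appointment, and the plan specifies no record of the drop time, the aspirate time or the interval between them

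*Combined protocol and SAP*

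**What the plan says.** **Timing of the drop.** Section 6.0 states that subjects "will be asked to administer the drops in the affected ear one hour prior to their appointment". Section 5.0 uses the same anchor: "the subject will be asked to keep a log of their medication use and to administer the ototopical medication one hour prior to their appointment". The Section 1.0 summary says that patients "will apply drops 1-hour prior to" the visit. All three fix the drop relative to the appointment or visit. None fixes it relative to the sample.

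**What happens in between.** At the follow-up visit, Section 6.0 has "the ear will once again be cleaned of any debris and a microscopic aspirate" taken afterwards. No duration is given for waiting or for cleaning.

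**Records kept by the subject.** Besides the log in Section 5.0, Section 6.0 says "A compliance card will be given to record adherence to three-time daily regiment for ten days", and Section 21.0 says "the subjects will be expected to complete a medication compliance / symptoms log". The fields of these forms are not described.

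**Data items.** The lists in Sections 5.0, 6.0 and 7.0 cover diagnosis, culture, symptoms, drainage, canal anatomy, treatment and outcome in varying detail. None names a drop time, an aspirate time or an interval.

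**Analysis.** Section 17.0 plans a Fisher's exact test of measured concentration against demographics and "extent of perforation, amount of aural drainage and treatment outcomes". It has no time variable, no acceptable sampling window and no rule for a sample taken off time.

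**The concern.** A concentration measured about an hour after a drop is instilled is likely to depend on how long ago that was. Section 2.0 hypothesises that self-administration delivers variable concentrations, and Section 4.0 plans to correlate concentration with anatomy, demographics and outcome. If ten subjects are sampled at ten different unrecorded intervals, the spread between them mixes two things: how well the drug reached the site, and when the fluid was taken. Nothing in the specified data would separate them.

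At stake are the interpretation of the hypothesised variability and the secondary correlations. The primary endpoint, which concerns sampling a known volume and developing the assay, is not invalidated by an unknown interval. The omission may be irreversible, because an aspirate time not noted at the visit may be lost, and a log kept by the subject would not supply it.

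**Working it through.** The plan states no figure on this point. N=10 comes without power, effect size or SD, so there is nothing to reproduce. The check has a textual part and an illustrative part.

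**1. Text.** Set side by side, the three timing statements (Sections 1.0, 5.0, 6.0) give

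interval = 60 min + wait after the appointment time + cleaning time ± self-timing error.

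The last three terms are not specified anywhere. Neither end of the interval, nor the interval itself, appears in the data lists of Sections 5.0, 6.0 and 7.0 or in the analysis statement of Section 17.0.

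**2. Fold change.** Assume first-order decline with half-life h. Samples taken d minutes apart in otherwise identical ears then differ by a factor 2^(d/h). The half-lives are assumptions.

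| Half-life (min) | 90 v 60 min after drop (d=30) | 120 v 60 min after drop (d=60) |
|---|---|---|
| 15 | 2^2 = 4.0 | 2^4 = 16 |
| 30 | 2^1 = 2.0 | 2^2 = 4.0 |
| 60 | 2^0.5 = 1.4 | 2^1 = 2.0 |
| 120 | 2^0.25 = 1.2 | 2^0.5 = 1.4 |

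**3. Noise or false association?** Section 17.0 does not say how concentration is to be categorised, so assume a median split and a factor dividing the subjects 5 v 5. Only a perfect split is then significant: two-sided Fisher p = 2/252 = 0.008, while 4/1 v 1/4 gives p = 0.21. The simulations used 20,000 trials per setting. The log SD is the natural-log spread from everything other than timing.

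- *No true patient effect, interval SD 15 min, timing unrelated to the factor.* The rejection rate is 0.8% to 0.9%, in line with the exact 2/252 = 0.8%. Timing creates no false associations here.
- *No true patient effect, one group sampled 30 min later on average.* For half-lives of 15, 30 and 60 min the rate rises to about 23%, 10% and 3% (log SD 0.5), or 10%, 3% and 1% (log SD 1.0).
- *True 4-fold effect, timing unrelated to the factor, log SD 0.5.* Power is about 69% with identical intervals. With an interval SD of 20 min it falls to about 14%, 40% and 59% for the same half-lives.
- *The same with log SD 1.0.* Power is already only about 16%, and falls to about 7%, 13% and 15%.

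**4. Share of total variability.** Section 3.0 cites a range of 1.2 to 602 mcg/g in 11 patients. ln(602/1.2) = 6.22. Dividing by 3.17, the expected range of 11 standard normal values, gives a log SD of 1.96. For intervals spread evenly over w minutes, the timing share of log variance is (ln 2/h)² × (w²/12) / 1.96².

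| Half-life (min) | w = 60 | w = 120 |
|---|---|---|
| 15 | 17% | 67% |
| 30 | 4% | 17% |
| 60 | 1% | 4% |

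The result runs from 1% to 67% depending on inputs that the documents do not give.

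**The case against.** **The lists do not prove that times go unrecorded.** This stands. The list in Section 5.0 is open-ended. Those in Sections 6.0 and 7.0 also leave out the ciprofloxacin concentration and the aspirate volume, which the study plainly will hold. The medication log is requested in the same sentence as the one-hour instruction and could carry a clock time. A reader might infer that the times will certainly not be collected; the documents support only that they are not specified. The log still would not give the time of the aspirate.

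**Timing differences need not become patient differences.** This also stands. A reader might infer that the planned comparisons would report timing effects as effects of anatomy or drainage. That requires timing to differ by factor, and nothing in the documents says it does. Otherwise timing widens the spread and hides real associations. Nor does Section 17.0 assert that all samples share one time after dosing; it is silent.

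**Self-administration is deliberate.** Section 3.0 faults the earlier study because its clinician-delivered drops do not reflect ordinary practice. Unobserved dosing is therefore part of the question and not a defect. Only the missing time record is at issue.

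**The size is assumed.** This stands. A reader might take the 67% as evidence that timing dominates. It rests on a 15-minute half-life and a two-hour spread of intervals, neither of which is in the documents. The log SD of 1.96 comes from ofloxacin in mucosa after clinician dosing, and leaves out the five patients with undetectable levels. With slow clearance and a narrow spread the effect is small.

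**Adjustment is weak at n=10.** This stands. A partial correlation with one covariate has 7 degrees of freedom and needs an absolute value of about 0.67 for two-sided p<0.05. A subset limited to a time band would be smaller than ten.

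**Conclusion.** The concern holds in a limited form. The drop is tied to the appointment, cleaning comes before the aspirate, and the plan specifies no record of either time or of the interval. Followed as written, it leaves timing inseparable from the variability in delivery that Section 2.0 sets out to show. For the patient-factor comparisons the main effect is loss of signal; false associations arise only if timing differs by factor.

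The size cannot be derived from the documents. The 2- to 16-fold difference for a 60-minute difference in interval is conditional on first-order decline with a half-life of 60 to 15 minutes. The simulated error rates and power also depend on the assumed median split, interval spread and log SD. The conclusion does not rest on any one of these values: without the times, the investigators could not show that they are in the case where timing is unimportant. This is worth correcting before the first follow-up visit, but it does not threaten the primary endpoint.

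**What to change.** In Sections 5.0, 6.0 and 7.0, add two recorded data items: the clock time of the last drop, asked at check-in, and the clock time of the aspirate, noted when it is taken.

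In Section 17.0, state that concentration will be listed and plotted against minutes since the drop for all ten subjects, and that overall variability and every patient-factor comparison will be interpreted in light of that interval. Any analysis adjusted for the interval should be labelled exploratory because n=10.

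The cost is two extra fields on the visit form and one descriptive display. There is no added procedure and no change to treatment. The drop time would still be self-reported, so the record reduces the ambiguity without removing it.
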